8.2.3. Electrocardiograms

- Triplicate 12-lead ECGs will be conducted as outlined in the SoA (see Section 1.3) to obtain heart rate, PR, QRS, QT, and QTc intervals. Refer to Section 7 for QTc withdrawal criteria and any additional QTc readings that may be necessary. As with vital signs, if ECG interval measurements are abnormal, an additional triplicate will be performed and recorded in the CRF.

8.2.4. Clinical Safety Laboratory Assessments

- See Section 10.2 for the list of clinical laboratory tests to be performed and to the SoA (Section 1.3) for the timing and frequency.
- The Investigator must review the laboratory report, document this review, and record any clinically relevant changes occurring during the study in the AE section of the CRF. The laboratory reports must be filed with the source documents. Clinically significant laboratory values are those deemed by the Investigator to be clinically significant resulting in further evaluation or treatment or those associated with an AE or clinical signs or symptoms.
- All laboratory tests with values considered abnormal and clinically significant during participation in the study or after the last dose of study intervention should be repeated until the values return to normal or baseline or are no longer considered clinically significant by the Investigator or Medical Monitor.
 - If such values do not return to normal/baseline within a period of time judged reasonable by the Investigator, the etiology should be identified, and Alexion notified.
 - All protocol-required laboratory assessments, as defined in Section 10.2, must be conducted in accordance with the laboratory manual and the SoA.
 - All laboratory values from non-protocol-specified laboratory assessments must also be recorded in the CRF.

8.2.4.1. Bowel and Urine Monitoring

Participant's bowel movements and urination will be monitored by the clinical staff. The clinical staff will record in the CRF each time a fecal and urine sample is collected. All urine and feces must be collected from Day -4 through Day -1, Day 1 through Day 8, Day 25 through Day 39.

8.2.4.2. Intake Monitoring

To support accurate quantification of copper/molybdenum intake, each participant's intake including both food and fluids will be monitored and recorded. Following each standardized meal, the clinical staff will record 100% completion of each meal including all liquids. If a participant is unable to eat 100% of the food for a given meal, the remaining food will be weighed and reported in the CRF to support accurate determination of copper/molybdenum as a fraction of the total meal. Similarly, if participants do not complete 100% of non-water fluids with meal, the remaining volume will be measured and recorded in the CRF. In the case of water intake, the staff will record daily water volume intake in the CRF.

8.2.5. Suicidal Ideation and Behavior Risk Monitoring

Suicidal ideation and behavioral changes will be recorded as adverse events and may, at the discretion of the Investigator, result in withdrawal of the participation from the study and urgent referral for psychiatric treatment.

8.2.6. Pregnancy

- Pregnancy data from female participants and female spouses/partners of male participants will be collected from the signing of the ICF and at the time points specified in the SoA. Any female participant who becomes pregnant while participating in the study will be discontinued from the study intervention. If a pregnancy is reported, the Investigator must immediately inform Alexion within 24 hours of awareness of the pregnancy and follow the procedures outlined in Section 10.4.
- For all Alexion products, both in development or post approval, exposure during pregnancy must be recorded and the pregnancy followed, until the outcome of the pregnancy is known (ie, spontaneous miscarriage, elective termination, normal birth, or congenital abnormality), even if the participant discontinues the study intervention or withdraws from the study. The corresponding infant must be followed for 3 months postpartum.
- Pregnancy is not considered as an AE (Section 10.4) unless there is a suspicion that the study intervention may have interfered with the effectiveness of a contraceptive medication. However, complications of pregnancy and abnormal outcomes of pregnancy are AEs and may meet the criteria for an SAE (eg, ectopic pregnancy, spontaneous abortion, intrauterine fetal demise, neonatal death, or congenital anomaly) (Section 8.3). Elective abortions without complications should not be reported as AEs.

8.3. Adverse Events and Serious Adverse Events

The definitions of AEs and SAEs can be found in Section 10.3.

All AEs will be reported to the Investigator or qualified designee by the participant (or, when appropriate, by a caregiver, surrogate, or the participant's legally authorized representative).

The Investigator and any qualified designees are responsible for detecting, documenting, and recording events that meet the definition of an AE or SAE and remain responsible for following up AEs that are serious, considered related to the study intervention or study procedures, or that caused the participant to discontinue the study intervention (see Section 7).

Procedures for recording, evaluating, follow-up, and reporting AEs and SAEs are outlined in Section 10.3.

8.3.1. Time Period and Frequency for Collecting AE and SAE Information

All AEs and SAEs will be collected from the signing of the ICF until the EOS Visit.

All SAEs will be recorded and reported to Alexion or the designee immediately and under no circumstance should this exceed 24 hours, as indicated in Section 10.3. The Investigator will submit any updated SAE data to Alexion within 24 hours of it being available.

Investigators are not obligated to actively seek AE or SAE data after conclusion of the study participation. However, if the Investigator learns of any SAE, including a death, at any time after a participant has been discharged from the study, and he/she considers the event to be reasonably related to the study intervention or study participation, the Investigator must promptly notify Alexion.

8.3.2. Method of Detecting AEs and SAEs

The method of recording, evaluating, and assessing causality of AE and SAE and the procedures for completing and transmitting SAE reports are provided in Section 10.3.

Care will be taken not to introduce bias when detecting AEs and/or SAEs. Open-ended and non-leading verbal questioning of the participant is the preferred method to inquire about AE occurrences.

8.3.3. Follow-up of AEs and SAEs

After the initial AE/SAE report, the Investigator is required to proactively follow up on each participant at subsequent visits/contacts. All SAEs will be followed up until resolution, stabilization, the event is otherwise explained, or the participant is lost to follow-up (as defined in Section 7.3). Further information on follow-up procedures is provided in Section 10.3.

8.3.4. Regulatory Reporting Requirements for SAEs

- Prompt notification of an SAE by the Investigator to Alexion is essential so that legal obligations and ethical responsibilities toward the safety of participants and the safety of a study intervention under clinical investigation are met.
- Alexion has a legal responsibility to notify both the local regulatory authority and other regulatory agencies about the safety of a study intervention under clinical investigation. Alexion will comply with country-specific regulatory requirements relating to safety reporting to the regulatory authority, Institutional Review Boards (IRBs)/ Independent Ethics Committees (IECs), and Investigators.

- Suspected unexpected serious adverse reactions (SUSARs) must be reported according to local regulatory requirements and Alexion policy and forwarded to Investigators as necessary.
- An Investigator who receives an Investigator safety report describing an SAE or other specific safety information (eg, summary or listing of SAEs) from Alexion will review and then file it along with the IB and will notify the IRB/IEC, if appropriate according to local requirements.

8.3.5. Adverse Events of Special Interest

There are no adverse events of special interest for this study.

8.3.6. Retained and Biobanked Sample

A single biobanked serum sample will be collected predose from each participant to serve as a retained sample during the study. Samples will remain on site and will be discarded following the completion of the clinical study report. The sample will not be used for genetic testing (see Section 8.7).

8.4. Treatment of Overdose

For this study, any dose of ALXN1840 greater than that specified in the protocol will be considered an overdose.

Alexion does not recommend specific treatment for an overdose.

Overdoses are medication errors that are not considered AEs unless there is an untoward medical occurrence resulting from the overdose.

In the event of an overdose or suspected overdose, the Investigator/treating physician should:

1. Contact the Medical Monitor immediately.
2. Closely monitor the participant for any AE/SAE.
3. Obtain a plasma sample for PK analysis if requested by the Medical Monitor (determined on a case-by-case basis).
4. Document the quantity of the excess dose as well as the duration of the overdose in the CRF.

Decisions regarding dose interruptions or modifications will be made by the Investigator in consultation with the Medical Monitor based on the clinical evaluation of the participant.

8.5. Pharmacokinetics

- Whole blood samples will be collected for the measurement of plasma concentrations of total molybdenum and PUF-molybdenum as specified in the SoA (Table 1) via ICP-MS. Samples collected within $\pm 10\%$ or 30 min, whichever is less, of the scheduled time will not be considered a protocol deviation.

- Instructions for the collection and handling of biological samples will be provided by Alexion. The actual date and time (24-hour clock time) of each sample will be recorded.
- Total molybdenum and PUF-molybdenum are surrogate measures of ALXN1840 and concentrations will be used to evaluate the PK of ALXN1840. Samples collected for analyses of plasma concentrations may also be used to evaluate safety aspects related to concerns arising during or after the study.
- Excess/additional samples may be stored for up to 5 years and used for PD and/or diagnostic biomarker development and research to understand the pathways associated with the mechanism of action of ALXN1840. These samples will not be used for genetic analyses (ie, RNA or DNA analyses).
- Genetic analyses will not be performed on these whole blood samples. Participant confidentiality will be maintained.
- See also Section 8.1.1 for details of molybdenum measured in food, drinks, urine, and feces.

8.6. Pharmacodynamics

Plasma total and PUF-copper, ceruloplasmin, ceruloplasmin-bound copper, and LBC will be assessed during the study.

Blood samples will be collected as described in the SoA (Table 1) for plasma isolation as per the Laboratory Manual. Plasma samples will be used for ICP-MS measurement of total copper and PUF-copper, ceruloplasmin, ceruloplasmin-bound copper, and non-ceruloplasmin-bound copper measured via PUF-copper, and/or LBC, or assessed via NCC/NCC_{corrected} methods at the time points indicated in the SoA (Table 1).

8.7. Genetics

Genetics will not be evaluated in this study.

8.8. Biomarkers

Please see Section 8.6 for details of total copper and PUF-copper, ceruloplasmin, ceruloplasmin-bound copper, and non-ceruloplasmin-bound copper as measured via PUF-copper, and/or LBC, or assessed via NCC/NCC_{corrected} methods, and Section 8.1.1 for details of copper measured in food, drink, urine, and feces.

8.9. Immunogenicity Assessments

Not applicable.

8.10. Health Economics Data and/or Medical Resource Utilization

Health economic and medical resource utilization parameters are not evaluated in this study.

9. STATISTICAL CONSIDERATIONS

9.1. Statistical Hypotheses

9.1.1. Primary Hypothesis

As this study is an exploratory study, no formal hypothesis testing is being conducted. Study results will be summarized using descriptive statistics.

9.2. Sample Size Determination

The sample size will be approximately 10 participants which will allow a general characterization of copper balance in response to ALXN1840.

9.3. Populations for Analyses

The population sets used for analysis are defined [Table 8](#).

Table 8: Populations for Analysis

Population	Description
Screened	All participants who sign the ICF.
Enrolled	All participants who sign the ICF, are eligible for the study, and are registered on Day -7 when participants are assigned a participant number.
Safety Analysis Set	All participants who receive at least 1 dose of ALXN1840 treatment.
Full Analysis Set	All participants who receive at least 1 dose of ALXN1840 treatment.
Per Protocol Set	All participants who received at least 1 dose of ALXN1840, had Baseline and all post Baseline values of copper intake (in food and drink) and copper output (in feces and urine), and were 100% compliant with study drug dosing. Participants with major protocol deviations that are likely to impact the primary endpoint analysis will be excluded from the Per Protocol (PP) Set. Major protocol deviations, and the PP Set, will be defined, documented, and agreed within Alexion prior to database lock.
Pharmacokinetic/Pharmacodynamic Analysis Set	All participants who have sufficient plasma samples to enable the calculation of PK parameters and provide PK/PD profiles.

Abbreviations: ICF = informed consent form; PD = pharmacodynamic; PK = pharmacokinetic.

9.4. Statistical Analyses

Statistical methods described in this section will be further elaborated in a separate Statistical Analysis Plan (SAP). Summary statistics will be computed and displayed by visit where applicable and will be presented by cohort (treatment experienced/treatment naïve), and overall Descriptive statistics for continuous variables will minimally include the number of participants, mean, standard deviation, minimum, median, and maximum. For categorical variables, frequencies, and percentages will be presented. Graphical displays will be provided as appropriate.

Analyses will be performed using the SAS® software Version 9.4 or higher.

9.4.1. Primary Analysis

The primary objective of this study is to demonstrate a net negative copper balance with daily repeat-dose ALXN1840 treatment (15 mg and 30 mg) in participants with WD.

The primary analysis will be performed using the Full Analysis Set. Average daily copper balance and molybdenum balance will be calculated over the following periods:

1. Day -4 through Day -1 representing predose baseline
2. Days 1 through 8 representing the ALXN1840 15 mg/day accumulation period
3. Days 25 through 28 representing the ALXN1840 15 mg/day steady-state period
4. Days 31 through 35, representing the ALXN1840 30 mg/day accumulation period
5. Days 36 through 39 representing the ALXN1840 30 mg/day steady-state period

As ALXN1840 is expected to increase copper excretion through fecal excretion, copper in stool will be critical for determining copper balance. Because stools can be irregular, assessment of copper and molybdenum balance will only include data up to the day of the final bowel movement. For example, for the period Day 1 through Day 8, if the final bowel movement occurs on Day 7, average daily copper balance for the Day 1 through Day 8 period will only include data from Day 1 through Day 7.

In the case of the 15 mg/day steady-state period (ie, Day 25 through Day 28), stool data collected on Days 29 - 30 samples may be used if needed to support assessments for the 15 mg/day dose. Use of these stool data (as needed) are consistent with an approximately 2-day gastrointestinal transit time.

In the case of stool irregularity, and to support assessment of copper output over time, bowel movement copper and molybdenum outputs may be averaged over the days between bowel movement (or start of study) to ensure an approximate value for each 24-hour period.

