Vitals sign measurements ^h	X			X			X				X		X									X		X	
12-lead ECG (triplicate)	X			X			X				X		X									X		X	
Adverse events	X		X	X	X	X	X	X	X	X	X	X	X	X	X	X	X	X	X	X	X	X	X	X	
Balance assessments																									
Cu/Mo-controlled meals ^v				X	X	X	X	X	X	X			X	X	X	X	X	X	X	X	X	X			
Light exercise regimen				X	X	X	X	X	X	X		X	X	X	X	X	X	X	X	X	X	X			
Urination and bowel movement monitoring, menstruation check ^s						X	X	X	X	X					X	X	X	X	X	X	X	X			
24-hour urine for Cu and Mo ^w						X	X	X	X	X					X	X	X	X	X	X	X	X			
Feces for Cu and Mo ^x						X	X	X	X	X					X	X	X	X	X	X	X	X			
Other																									
Concomitant medication and non-pharmacologic therapy/procedure	X		X	X	X	X	X	X	X	X	X	X	X	X	X	X	X	X	X	X	X	X		X	

^a Within 42 days of ALXN1840 administration. Details of procedures that may be performed by sites designated as “screening sites” (only in the US) are detailed in Section 8.

^b Participants will be admitted to the clinical research unit (CRU) at least 10 hours prior to enrollment and initiation of copper- and molybdenum-controlled diet.

^c At the CRU’s discretion, participants may remain in the CRU or be readmitted on Day 22 with all procedures starting on Day 23.

^d Unscheduled study visits may occur at any time during the study and may include any study procedure as deemed necessary by the Investigator.

^e Participants are required to return to the CRU Day 54+/-2; participants will be discontinued from ALXN1840 medication by their physician at the latest by the Day 54 follow-up.

^f Discharge from the unit may occur after completion of all procedures on Day 9 and on Day 40 and after the Investigator has reviewed all safety assessment (including safety laboratory tests) and confirmed that the participant is appropriate for discharge.

^g A single outpatient visit or phone call and safety laboratory assessment should occur between Day 14 and Day 18. A phone call may take place on a different day than the blood draw within the Day 14 through Day 18 period.

^h If needed to confirm menopause.

- ⁱ Parameters include age and sex. Race and ethnicity will be collected where permitted by local regulations.
- ^j Wilson disease history will include diagnosis date, method of diagnosis, history of cirrhosis, details of any previous liver biopsies performed, and treatment received.

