Collection periods for feces and urine will vary in duration from 3 to 15 days to support assessment of both copper and molybdenum balance before and at steady state for both 15 mg and 30 mg. Equilibration periods on copper/molybdenum-controlled diets will be a minimum of 48 hours. Copper balance will be calculated as the mean daily copper balance over each of the 4 collection periods. The interpretation of copper balance will be based on the criteria established by [Hill, 1986](#) when undertaking copper balance studies with zinc treatment. For assessment of ALXN1840 effect on copper balance, the time period for analysis will take into consideration the average bowel transit of approximately 40 hours (male: 33 hours; female: 47 hours) ([Camilleri, 1986](#); [Metcalf, 1987](#)).

Throughout the inpatient periods, participants will remain on a copper-controlled diet. Meal portions will be weighed, and meal sizes will be appropriate to support male and female caloric consumption. Participants will be encouraged to complete 100% of all meals throughout the inpatient period to support quantification of copper and molybdenum intake. If participants are unable to complete the full meal, the uneaten portion will be weighed to allow calculation of meal fraction, and copper and molybdenum intake will be adjusted based on the fractional intake

of the meal. In addition to food, fluid intake and type will be measured and recorded each day. Samples of all meals and fluids will be sent for bioanalysis to support accurate quantification of copper and molybdenum in fluids. In the event that items cannot be accurately quantified, items may be balanced during pretreatment period and post-treatment period to support the change from baseline assessment.

During the inpatient collection periods, daily urine will be pooled (24-hour collection) with volumes recorded for each 24-hour period; participants will be strongly encouraged to void within 2 hours of completion of each 24-hour period (ie, dosing time). Stool samples will be individually collected and each sample will include a collection date, time, and weight.

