Finally, preclinical data from ALXN1840 ADME study suggest the potential for molybdenum accumulation in the liver of participants with WD; therefore, an assessment of molybdenum balance will help determine whether steady state has been reached as defined by a molybdenum balance of neutral during the collection period. Because molybdenum is a necessary micronutrient and serves as a cofactor for a number of enzymes and may exist in intracellular stores, small variations in molybdenum balance could be due to molybdate rather than ALXN1840.

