7.2.1. Primary Analysis

Based on the ALXN1840 mechanism of action, the primary objective of this study is to demonstrate a net negative copper balance with daily repeat-dose ALXN1840 treatment (15 mg and 30 mg) in participants with WD.

The primary analysis will be performed using the FA Set. Average daily copper balance and molybdenum balance will be calculated over the following periods:

- Day -4 through Day -1 representing pre-dose Baseline
- Days 1 through 8 representing the ALXN1840 15 mg/day accumulation period
- Days 25 through 28 representing the ALXN1840 15 mg/day steady-state period
- Days 31 through 35 representing the ALXN1840 30 mg/day accumulation period
- Days 36 through 39 representing the ALXN1840 30 mg/day steady-state period

Copper balance is defined by the difference in copper input and copper output. A negative Copper balance will indicate greater copper output than copper intake. Copper input is defined as the sum of all copper input as measured in all food and fluids over the specified period. Copper output is defined as the sum of all copper output as measured in urine and feces over the specified collection period. Many of the copper inputs and outputs will be collected with technical replicates and the mean of the replicates will be utilized in the analysis. The average daily copper balance is calculated as the difference in copper input and copper output during the specified period, divided by the total number of days in that period.

As ALXN1840 is expected to increase copper excretion through fecal excretion, copper in stool will be critical for determining copper balance. Because the timing of bowel movements can be irregular, assessment of copper and molybdenum balance will only include data up to the day of

the final bowel movement. For example, if the participant does not have a bowel movement on Day 8, then average daily copper balance for the Day 1 through Day 8 period will only include data from Day 1 through Day 7.

In the case of the 15 mg/day steady-state period (ie, Day 25 through Day 28), stool data collected on Days 29 - 30 samples may be used if needed to support assessments for the 15 mg/day dose. Use of these stool data (as needed) are consistent with an approximately 2-day gastrointestinal transit time.

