In the case of stool irregularity, and to support assessment of copper output over time, bowel movement copper and molybdenum outputs may be averaged over the days between bowel movement (or start of study) to ensure an approximate value for each 24-hour period.

The daily copper balance for each subject will be plotted as will the mean daily copper balance.

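### Balance windows start on a fixed day but are cut at the last stool, which on average shifts absolute copper balance toward negative unless stools are daily or the optional averaging clause is applied; the Days 29-30 stool provision is undefined

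*Protocol*

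**What the plan says.** Both documents define five windows by calendar day: Days -4 to -1, 1-8, 25-28, 31-35 and 36-39, that is 4, 8, 4, 5 and 4 days. Four rules then act on them.

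- **End cut** (Protocol 9.4.1, repeated in SAP 7.2.1): "assessment of copper and molybdenum balance will only include data up to the day of the final bowel movement". The worked example drops Day 8 when the last stool of Days 1-8 falls on Day 7. No rule treats the start of a window.
- **Divisor** (SAP 7.2.1): input minus output is "divided by the total number of days in that period". Whether this means the nominal or the shortened length is not said.
- **Days 25-28** (both documents): "stool data collected on Days 29 - 30 samples may be used if needed to support assessments for the 15 mg/day dose". The stated reason is a transit time of about two days.
- **Averaging** (both documents), for irregular stools: "outputs may be averaged over the days between bowel movement (or start of study) to ensure an approximate value" for each 24 hours.

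Protocol 4.1 adds that "the time period for analysis will take into consideration the average bowel transit of approximately 40 hours". On collection, Protocol 8.2.4.1 states "All urine and feces must be collected from Day -4 through Day -1, Day 1 through Day 8, Day 25 through Day 39", while the Schedule of Activities row "Feces for Cu and Mo" also marks Day 40. SAP 4.1 declares no change from the protocol.

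**The concern.** In a fixed window, stool carried in at the start is offset on average by stool formed inside the window and passed after it. The cut removes only one side of that exchange. The effect is plainest where windows adjoin (Day -1 to Day 1, and Day 35 to Day 36). If the last day of the first window is stool-free, its intake and urine count in neither window, but its faecal copper counts in the second.

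Protocol 9.4.1 and SAP 5.1.1 state the primary objective as demonstrating a net negative balance, so a rule that at constant output can only err toward negative needs attention. Molybdenum follows the same rules, and Protocol 4.2 judges whether "steady state has been reached as defined by a molybdenum balance of neutral during the collection period". Overstated stool molybdenum would work against detecting accumulation. The Days 29-30 provision bears on the 15 mg versus 30 mg steady-state comparison.

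**Working it through.** The plan states no figure for this effect, so there is none to reproduce. Window lengths come from Protocol 9.4.1 and the 40-hour transit from Protocol 4.1. Stool patterns are assumptions, since the documents give no frequency.

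**Model.** Faecal copper is formed at a constant 1 unit per day, and each stool carries everything since the previous one. If the last stool before the window came g days before the window's eve (g = 0 if on the eve), and the last stool in the window is on its day k, counted faecal copper per kept day is (k + g)/k. The excess is g/k, which is at least 0.

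**Example: 4 days, stool every 2 days.** Stools on window days 1 and 3: g = 1, k = 3, excess 1/3. Stools on days 2 and 4: g = 0, excess 0. Mean (1/3 + 0)/2 = 16.7%.

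**Example: 4 days, stool every 3 days.** Days 1 and 4: 2/4. Day 2 only: 1/2. Day 3 only: 0. Mean (0.5 + 0.5 + 0)/3 = 33.3%.

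**All windows.** Regular patterns are averaged over phase and random daily stools over all sequences. Windows with no stool are excluded from the cut rows; under the rule their balance is undefined.

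| Mean overstatement of faecal copper | Daily | 0.9/day | 0.75/day | Every 2 days | Every 3 days |
|---|---|---|---|---|---|
| 4-day, cut | 0% | 2.9% | 9.5% | 16.7% | 33.3% |
| 5-day, cut | 0% | 2.3% | 7.4% | 10.0% | 23.3% |
| 8-day, cut | 0% | 1.4% | 4.4% | 7.1% | 13.7% |
| Any length, uncut | 0% | 0% | 0% | 0% | 0% |

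The uncut row shows that the one-sided cut is the cause.

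**If the divisor is the nominal 4 days**, faecal copper is right on average, but intake and urine from the dropped days are lost. At true zero balance the shift is -E[g]/4 = -2.8%, -8.3%, -12.5%, -25% of daily faecal copper for the four non-daily patterns, in the same direction.

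**In mg.** The documents give no human faecal copper value. At an assumed 1 mg/day (range 0.5 to 2), the 4-day cut shifts balance by -0.03 (-0.01 to -0.06), -0.10 (-0.05 to -0.19), -0.17 (-0.08 to -0.33) and -0.33 (-0.17 to -0.67) mg/day.

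**Days 1-8 when output rises by a fraction r after dosing.** Pre-dose stool dilutes the rise for about 40/24 = 1.67 days, so the net error is E[g/k] - r × 1.67 × E[1/k]. For stools every 2 days, E[1/k] = (1/7 + 1/8)/2 = 0.134, and the error is zero at r = 0.0714/(1.67 × 0.134) = 32%. The four crossing points are 7%, 20%, 32% and 57%. Below them the error is toward negative, above them toward positive.

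**Days 25-28 under different readings of Days 29-30** (overstatement of faecal copper):

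| Reading | Daily | 0.9/day | 0.75/day | Every 2 days | Every 3 days |
|---|---|---|---|---|---|
| First later stool if none on Day 28; intake, urine and days extended to match | 0% | 2.7% | 8.0% | 10.0% | 23.3% |
| Same stool, divisor left at 4 days | 0% | 5.5% | 15.4% | 25.0% | 50.0% |
| All Days 29-30 stool, divisor 4 days | 50% | 50% | 50% | 50% | 50% |

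The last row is six days' output over four: 6/4 = 1.5. The trigger in the first two rows is supplied here; the plan gives none. Subtracting the cut-only result for Days 36-39, the false 15 mg minus 30 mg difference in faecal copper for the four non-daily patterns is -0.2, -1.5, -6.7, -10.0 points (row 1), +2.6, +5.9, +8.3, +16.7 (row 2) and +47.1, +40.5, +33.3, +16.7 (row 3). The sign depends on the reading.

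**The case against.** The strongest reply is that the plan already holds the remedy. Averaging stool output between bowel movements is provided for exactly the irregularity that creates the bias. If it is carried into the period means, it could remove the bias for windows starting on Days 1, 31 and 36, where the previous stool is normally on record. That stands, and it is why the figures above hold only if the clause is not used. It does not settle the matter. The clause is permissive, is absent from the SAP formula, and cannot work for Days -4 and 25, because bowel monitoring and collection begin on those days.

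Second, the bias is zero for any participant with a stool on the day before the window: 90% and 75% of windows at 0.9 and 0.75 stools per day. Scheduled light exercise is meant to promote regularity (Protocol 5.3). That also stands; at 0.9/day the cut costs 1% to 3%.

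Third, the study is exploratory with no hypothesis test, and Protocol 4.1 ties interpretation of balance to criteria from a cited zinc study. A reader might infer that the sign of a small balance decides the result, or that a negative finding would be an artefact. The documents do not support either: those criteria are not reproduced, and stool frequency is not given.

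A reader might also infer that change from baseline is protected. In expectation the bias cancels between 4-day windows only if output, bowel habit and handling are the same in both. If averaging corrects Days 36-39 while baseline keeps its bias, baseline faecal copper stays overstated and the change is shifted against the drug.

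Finally, the copper percentages do not transfer to total molybdenum output, since the protocol describes urinary excretion of molybdate. Only the faecal share is affected.

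**Conclusion.** The point holds in a bounded form. As written, the end cut overstates faecal copper on average whenever stools are less than daily, never understates it at constant output, and so moves absolute balance toward the stated objective. The size is 3% to 33% of faecal copper in 4-day windows, 2% to 23% in the 5-day window and 1% to 14% in the 8-day window across the assumed patterns, and nil with daily stools. This rests on constant output, on the assumed patterns, and on averaging not being applied to period means. If output rises after dosing, Days 1-8 can err either way. The effect on the study's conclusion cannot be sized from the documents.

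The Days 29-30 provision is a separate gap. It has no trigger and no rule for intake, urine or divisor, and one permitted reading adds 50% to faecal copper even with daily stools.

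**What to change.** In SAP 7.2.1, with a matching protocol change:

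1. Replace *may* with *will* in the averaging clause and put it in the primary formula. Spread each stool's copper and molybdenum over the days since the previous stool, and count only the share inside the window.
2. Sum intake, urine and allocated stool over the same days, and use those days as the divisor.
3. Let a Day 29-30 stool contribute to Days 25-28 only its allocated share.
4. Keep the end cut only where no later stool is collected, normally Days 1-8 and 36-39.
5. For future participants, record the time of the last stool before Day -4 and before Day 25.
6. For participants without that time, use the uncut fixed 4-day window, with no allocation at either end and no Day 29-30 stool. It is unbiased on average but adds between-participant SD of 12%, 24%, 0% and 35% of faecal copper for the four non-daily patterns. Show a stool-to-stool window only as a sensitivity analysis: it keeps a mean of 2.9, 2.7, 2.5 and 2.0 days, below the plan's 3-day minimum.
7. Reconcile Protocol 8.2.4.1 (collection to Day 39) with the Schedule of Activities (Day 40 marked).
8. State that Days 1-8 includes stool formed before dosing.

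The cost is SAP wording, minor programming and a small case report form addition; no extra participants are needed. Stool times and weights are already recorded. Even allocation is exact only at constant output and is approximate while output is changing. Because this SAP governs the second and later interim analyses, pre-window stool times not recorded for participants already studied cannot be recovered, so the rule should be settled before the next data cut.
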